All eligible women, in whom UFE is not inherently contraindicated, will be screened based on the following Inclusion/Exclusion criteria during their initial clinic appointment to discuss UFE. This will consist of a standardized questionnaire administered with participation from the primary physician and utilize standardized teach-back techniques to ensure patient understanding [24].

Inclusion: Women aged 20-50 years, undergoing UFE for symptomatic fibroids.

Exclusion: Women aged <20 or >50 years, those pregnant or actively attempting to conceive, those deemed mentally impaired to make their own medical decisions, previous documented allergy to dexamethasone, those currently taking daily steroids for any reason, those with diabetes or deemed to be pre-diabetic, those with contraindications for angiography, and prisoners.

9. Number of Subjects*

The power calculation is primarily based on the paper from Kim et al, which evaluated the effect of IV dexamethasone for treatment of post UFE pain and PES [3]. Based on this study, the mean Visual Analogue Scale for the Dexamethasone group was 2.89 (SD 1.09) compared to 3.91 (SD 2) for controls. However, in contrast to the reference study, the proposed study utilizes intraarterial drug delivery directly into uterus instead of IV route drug, which results in higher concentration in the uterus [25-27]. For a low flow organ such as uterus, intraarterial delivery of a low clearance drug such as dexamethasone will result in a regional advantage of 10-25 times compared to IV or oral delivery as shown by Daemen et al. [25]. Given the significantly enhanced organ drug concentration in the uterus, an increase in effect size of at least 50% is expected with intraarterial drug administration compared to IV route. To detect a difference 50% larger between control group and intervention group, using a two-sample t test with significance level of 0.05, sample size of 21 per group will provide us with 86% statistical power to detect such an effect size.

10. Study-Wide Recruitment Methods*

As with the discussion of Inclusion/Exclusion criteria, participants will be introduced to the study at the time of their initial clinical visit (referred for UFE through typical channels), and once they have already met criteria for undergoing a UFE for symptomatic fibroids. The patients will not be actively recruited for this study, per say, but will be offered admission to it providing they meet criteria.

11. Study Timelines*

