We intend to start the study by 10/2020 and to complete recruitment in 2 years, completing in 10/2022

Unless a patient chooses to opt-out of the study, a participant's duration will be limited to a total of 15 days beyond the procedural date. This will include periodic assessments of a subjective and objective measure, as outlined later in this proposal.

[figure not shown]
Enrollment and data analysis will be conducted on a rolling basis and deemed complete upon either meeting the primary endpoints (detailed below) or in the face of severe adverse events related to the procedural modification (detailed below).

12. Study Endpoints*

Primary end point of this study is post procedure pain. As such, pain is measured using a modified Visual Analogue Score (VAS), a numerical rating system that each patient assigns to their level of pain, at a particular time [28]. The study endpoints will include qualitative and quantitative collection of data. Pain following UFE is subjective and unique to each patient and can be based on the location, number of the fibroid(s) and the volume of fibroid(s). A modified VAS, termed *UFE Pain and PES Survey*, will be utilized to assess pain prior to and following the procedure (Pre, immediately after the procedure, and periodically for the next 13 days, as described below). Our primary endpoint will be a 3-point decrease in the UFE Pain & PES score between test and controls.

Secondary endpoints will include assessment of PES based on the measurement of nausea, vomiting, subjective fevers or chills, subjective data obtained from return to work times and readmission rates. This will be assessed in part using our *UFE Pain and PES Survey*, which includes a previously validated numerical scoring system

(0-3) to categorize nausea and vomiting, as well as a “Yes” or “No” scoring system to evaluate subjective fevers or chills.

13. Procedures Involved*

The Uterine Artery Embolization procedure with the proposed intervention is detailed below, italicized section denotes the interventions which are additions to the standard of care. The procedure is separated into Pre-Procedure Assessment and Imaging, Uterine Artery Embolization Procedure, and Post-Procedure Assessment and Imaging.

Pre-Procedure Assessment and Imaging:

- All accepted UFE study participants will be initially assessed using the attached UFE Pain & PES Survey to ascertain their current baseline pain.

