- Current medication requirements (e.g. OCPs, NSAIDs, narcotics, anti-emetics) will also be assessed at this time.
- Basic laboratory studies will be conducted at this time. This will include a Complete Metabolic Panel (CMP), Complete Blood Counts (CBC), Hemoglobin A1c, and qualitative urine pregnancy test (UPT).
- Each patient will further undergo (or have recent) pre-procedural imaging to determine fibroid burden, approximate volume, and arterial anatomy. This should be an MRI of the pelvis.

Uterine Embolization Procedure:

No changes are proposed to the standard UFE procedure except for the intraarterial delivery of dexamethasone.

Pre-UFE patients will receive the following medications for conscious sedation, pain control and nausea/vomiting during the procedure as per the standard departmental protocol, unless contraindicated:

- 50-300 mg IV Fentanyl
- 0.5- 3.0 mg IV Versed
- 30 mg IV Toradol
- 1 g IV acetaminophen

Procedure technique:

No changes are proposed to the standard UFE procedure except for the intraarterial delivery of dexamethasone.

Common femoral or radial artery access is used for the procedure. Using a combination of base catheters, microcatheters and different wires, each uterine artery is catheterized and angiograms are performed. *Following this, prior to embolization, 5 mg of IV dexamethasone or placebo are injected via the microcatheter placed in the uterine artery.* This is followed by particle embolization using particles of size ranging from 500-1000 μ M, until near stasis as per standard technique. The same procedure is then repeated on the contralateral uterine artery. Finally, catheters and sheaths will be removed and hemostasis achieved at the access sites using closure device or manual compression. Patients will be admitted to the general medicine ward for overnight observation.

Post-UFE patients will receive the following pain/anti-emetic regimen post procedure:

Inpatient Medications

- 30 mg IV Ketorolac q6h
- 650 mg PO Acetaminophen q6h (continued for 4 days post procedure)
- 0.2 mg demand dose, 10 minute lockout, 1.2 mg/hour, Hydromorphone PCA
- 4 mg IV Ondansetron q6h PRN

Discharge Medications

- 650 mg PO Acetaminophen q6h (4 days post procedure, then q12h)
- 800 mg PO Ibuprofen q6h (4 days post procedure, then q12h)
- 5/325 mg PO Percocet q6h PRN
- 100 mg PO Docusate Sodium (Colace) q12h (4 days post procedure, then PRN)
- 4 mg SL Ondansetron q6h PRN

Post-Procedure Assessment and Imaging:

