A single computer system managed by the Pharmacology Research Coordinator, [name], will be maintained to ensure blinding of the cohorts. Collected data will be analyzed by [name], and done so prior to unblinding.

16. Provisions to Monitor the Data to Ensure the Safety of Subjects*

All data will be analyzed as it arrives and on a rolling basis by the primary physicians and researchers directly involved in this study, to ensure that the clinical findings and participant reported responses to the Pain & UFE Survey are not deviating in a way that could lead to undue harm.

As stated previously, all participants will be admitted to the hospital for observation for the first 24 hours and discharged with 2-week clinical follow-up in place and the contact information of a research team member. All participants will be contacted daily for the first 3 days, then at 7 and 14 days following the procedure. Any adverse effects of safety issues would be discovered in this follow up.

At 6 months we will analyze the interim data for any difference in the efficacy of treatment between the groups. All data will be analyzed using IBM SPSS software. We will use Student's T test for analysis of continuous variables, Chi square test for categorical variables with significance level set at two tailed p value of <0.05.

Although we expect that this trial exposes the participants to minimal risk, we consider the following statistically-significant differences between the two arms to be grounds for immediate trial termination: excessive abnormal uterine bleeding, infection, and sepsis.

17. Withdrawal of Subjects*

Subjects will be immediately withdrawn if it is deemed at any time prior to the procedure date that they fall into any of the previously outlined Exclusion criteria, suffer an intra-procedural adverse reaction to the use of dexamethasone, or willingly choose to leave the trial at any time.

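### Pain and QOL are compared by an unadjusted t test although baseline pain, baseline QOL and MRI fibroid volume are collected; prespecified ANCOVA would probably add precision at little cost

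*Combined protocol and SAP*

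**What the plan says.** - **Method.** Section 16 plans Student's "T test for analysis of continuous variables", with chi-square for categorical variables and "significance level set at two tailed p value of <0.05". The sentence follows the one on the 6-month interim look. It appears to cover the final analysis too, because it is introduced as applying to all data and no other method is given anywhere.
- **Sample size.** Section 9 rests on the same test: "using a two-sample t test with significance level of 0.05, sample size of 21 per group will provide us with 86% statistical power".
- **Prognostic factors.** Section 12 says that pain after UFE is subjective and "can be based on the location, number of the fibroid(s) and the volume of fibroid(s".
- **Baseline data.** Under Section 13, participants are "initially assessed using the attached UFE Pain & PES Survey to ascertain their current baseline pain", and a further score is taken at Time 0, immediately before the procedure. Each patient has "pre-procedural imaging to determine fibroid burden, approximate volume, and arterial anatomy", by pelvic MRI, and completes the QOL questionnaire before the procedure.
- **Randomisation.** The Study Design part of Section 13 specifies blocks of 8 and states no stratification factor.

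No section mentions ANCOVA, regression or any other baseline adjustment.

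**The concern.** The protocol names factors that may drive the primary outcome and measures them before treatment, then leaves them out of the comparison. Any outcome variance that they explain stays in the error term. Nothing in the design balances them either. With 21 per arm, the between-arm difference in the mean of any one covariate has a standard deviation of sqrt(2/21) = 0.31 covariate SDs, so noticeable chance imbalance in fibroid volume or baseline pain is quite possible. An unadjusted result from an imbalanced trial is harder to interpret.

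Precision matters here because the trial has 42 patients and its power depends on enlarging the reference study's effect by half. At the reference study's own difference, power is only about 52%.

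**Working it through.** **Inputs (Section 9).** In the reference study, "the mean Visual Analogue Scale for the Dexamethasone group was 2.89 (SD 1.09) compared to 3.91 (SD 2) for controls". The design enlarges the difference by 50%, with 21 per arm and alpha 0.05; Section 16 makes the test two-sided.

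**Step 1: reproduce the plan's power.**
- Reference difference: 3.91 − 2.89 = 1.02. Design difference: 1.5 × 1.02 = 1.53.
- SD: sqrt((1.09² + 2²)/2) = 1.611. Standardised effect: 1.53/1.611 = 0.95.
- Standard error: 1.611 × sqrt(2/21) = 0.497.
- Power of the t test (noncentral t, 40 df): 85.2%. The normal approximation gives 86.8%. The stated 86% is reproduced.
- At the reference difference of 1.02, t test power is 51.7%.

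**Step 2: ANCOVA with two covariates for pain.** If the covariates jointly explain a share R² of the within-arm variance, the residual SD is 1.611 × sqrt(1 − R²). Estimating k covariates in 2n patients multiplies the variance of the treatment contrast by about 1 + k/(2n − k − 3). For k = 2 and n = 21 this is 1 + 2/37 = 1.054. The degrees of freedom fall to 38. The documents give no value for R², so every value below is an assumption.

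| R² (assumed) | Variance relative to t test | Power at 1.53 | Power at 1.02 |
|---|---|---|---|
| Unadjusted t test | 1 | 85.2% | 51.7% |
| 0% | 1.054 | 83.2% | 49.5% |
| 10% | 0.90 × 1.054 = 0.949 | 86.9% | 53.7% |
| 20% | 0.80 × 1.054 = 0.843 | 90.4% | 58.6% |
| 30% | 0.70 × 1.054 = 0.738 | 93.7% | 64.4% |

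Break-even is where (1 − R²) × 39/37 = 1, so R² = 2/39, about 5% (a multiple correlation of about 0.23). At 10%, 20% and 30%, the adjusted analysis at 1.53 matches an unadjusted trial of about 22, 25 and 28 per arm.

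**Step 3: QOL.** Assume a correlation of 0.5 between the pre-procedure and follow-up scores, with equal SDs. In units of the raw variance:
- raw comparison: 1;
- change score: 2 × (1 − 0.5) = 1;
- ANCOVA: 1 − 0.5² = 0.75.

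ANCOVA variance is therefore 25% lower than either alternative. With the one-covariate cost, 1 + 1/38, the ratio is 0.75 × 39/38 = 0.770, or about 23% lower.

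**The case against.** The best defence of the plan is that an unadjusted t test is valid and unbiased under randomisation and matches the test behind the sample size. That is correct, so this point concerns efficiency and not an error.

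Second, the gain may be small. At 10% of variance explained, power rises by only 1.7 points, and with useless covariates it falls by 2. Pain from fibroids before the procedure may predict ischaemic pain after embolization only weakly: at a correlation of 0.2 it explains 4%, just under the two-covariate break-even. Most of the gain for pain might then have to come from fibroid volume, for which the documents give no figure. This objection stands as a limit on the size of the benefit. It does not remove the case, because the likely loss is small and bounded while the possible gain is larger.

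Three stronger readings are tempting but unsupported:

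- A reader might infer that adjustment is free. It needs no new data, but in 42 patients each covariate costs about one power point if it explains nothing.
- A reader might infer that the protocol asserts that pain depends on fibroid volume. Section 12 says only that it can.
- A reader might take the 3-point decrease in the primary endpoint as change from Time 0 and conclude that a noisy change score will be tested. Section 12 words the decrease as between test and control patients, and Section 9 powers on group mean scores. No change-score analysis of pain is planned.

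**Conclusion.** The point holds as a low-cost improvement. Section 16 gives only an unadjusted t test for continuous outcomes although suitable baseline covariates are collected. The planned test remains valid; the cost is lost precision and unadjusted chance imbalance.

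For pain at the design difference, two-covariate ANCOVA changes power by between −2.0 points (nothing explained) and +8.5 points (30% explained). At 1.02 the range is −2.2 to +12.7 points. For QOL, variance falls by roughly a quarter at a correlation of 0.5. That the adjustment is missing is certain from the text. The size of the benefit is not: it rests on assumed R² and correlation values and on the common SD of 1.61 from the reference study.

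**What to change.** Amend Section 16 as follows:

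1. **Pain.** Make the primary analysis an ANCOVA of the post-procedure pain score on arm, pre-procedure pain score and total fibroid volume from the pre-procedure MRI. State which pre-procedure score is the baseline (Time 0 or the earlier survey). Section 13 schedules 12 post-procedure scores (3 + 3 + 2 + 3 + 1) and none is named as primary, so the model must be tied to whichever time point or summary is chosen.
2. **QOL at 1 and 3 months.** Use ANCOVA on arm and pre-procedure QOL score.
3. **Discipline.** Fix the covariates, and any transformation of volume, before unblinding. With 42 patients, add no more than these. Keep the unadjusted t test as a sensitivity analysis.

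The cost is a few sentences of text, two degrees of freedom for pain and one for QOL. No extra data are collected. The downside is about 2 power points for pain if the covariates turn out to explain nothing.

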All patients will have a routine 2 week post-procedural phone call to review their symptoms, 1 month clinic visit and then 3 month clinic visit after MRI imaging.

All data collected from the Surveys will be stored and analyzed as described elsewhere in this proposal. Again, we expect that this study will reach its recruitment goal and Primary Endpoint in approximately 2 years.

To evaluate specific aim 1:

Pain will be assessed using 11 point visual analog scale as below:

The visual analog pain score will be documented as follows:

- Time 0 Immediately prior to the procedure
- 1 hour intervals for the first 3 hours
- 3 hour intervals for the next 9 hours
- 6 hour intervals for the next 12 hours
- Daily, for the next 3 days
- Once at day 7

First 3 of those surveys will be done in the recovery area. The amount of narcotic use from PCA pump will also be recorded.

To evaluate specific aim 2:

Post embolization syndrome will be assessed as reporting of nausea, vomiting and pain scores, that will be assessed at least twice during the day of the procedure and then daily for the next 3 days and then at 7 days. We will utilize our previously mentioned UFE Pain and PED Survey.

To evaluate specific aim 3:

Symptom relief, patient satisfaction and fibroid volume change will be measured through the completion of a UFE health-related quality of life (QOL) survey, UFE QOL Survey, prior to the procedure and then at 1 month and 3 month after procedure.

Uterine volume will be compared from the pre-procedure and 3 month post procedure MRI using volumetric software.

14. Data and Specimen Banking*

No specimen will be collected or stored. Data will be kept in password protected, HIPAA compliant University approved Box folder, accessible only to investigators.

15. Data Management*

All data will be stored, accessed, and analyzed utilizing server and computer workstations previously approved as HIPAA compliant. Data will be kept in password protected, HIPAA compliant University approved Box folder, accessible only to investigators. Anonymized data will include age, pre and post MRI imaging, UFE Pain & PES Survey, narcotic use, vital signs, subjective reports of nausea, vomiting, daily dietary intake, bowel movements, length of hospital stay, readmission rate, and days to return to baseline.

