Associate Program Director of the Interventional Radiology Residency and Fellowship Programs

[name] [name]

Assistant Professor of Vascular and Interventional Radiology

[name]

Assistant Professor of Vascular and Interventional Radiology

IRB Study Number: Version: 05282020 Date: 05/28/2020

[name], PhD
Vascular and Interventional Radiology Resident

[name]
Diagnostic Radiology Resident

Other research personnel:

[name] PharmD, BCPS
Clinical Research Pharmacist
University of Miami Sylvester Comprehensive Center

[name], APRN
Vascular and Interventional Radiology

[name]
Research Coordinator
Vascular and Interventional Radiology

26. Prior Approvals

All approvals have been granted by the Vascular and Interventional Radiology Department at the University of Miami for this study. This includes funding for a dedicated Research Coordinator and the costs associated with compounding the materials required in the study.

27. Recruitment Methods

Recruitment will occur at the first clinical encounter between Physician and Patient in the IR clinic. Patients considering UFE generally placed in contact with the Vascular and Interventional Radiology team through a standard physician referral system. Referring physicians typically include Obstetric/Gynecologic specialists, Hospitalist, Emergency Physicians, and Primary Care Practitioners. Patients are seen in clinic prior to determining candidacy for the procedure and it is at this time that the research is introduced. If deemed a candidate for a UFE (please see listing of Inclusion/Exclusion Criteria), participants will be introduced to the study utilizing the same simplified language and pelvic models currently utilized to describe the

procedure, and the risks and benefits associated with such. As mentioned, standard teach-back techniques will be employed to gauge participant understanding.

28. Local Number of Subjects

We anticipate that there will be approximately 21 local participants in each arm of this trial. As described above, this number appears to be the minimum required to ensure adequate statistical power. We anticipate to take approximately 2 years to recruit the patients.

29. Confidentiality

- On a University of Miami electronic device (e.g. encrypted, password-protected computer).
- On a cloud-based storage system that is approved by the University of Miami.
- JHS Secured SharePoint.

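### Section 16 does not say which test applies to the ordered 0-3 nausea and vomiting scores, and one permitted choice, an unordered chi-square, would lose power against a consistent shift

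*Combined protocol and SAP*

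**What the plan says.** - **Endpoint.** Section 12: "Secondary endpoints will include assessment of PES based on the measurement of nausea, vomiting, subjective fevers or chills". The scale is described there as a validated numerical score, "0-3) to categorize nausea and vomiting". Fever or chills is a yes/no item.
- **Tests.** Section 16 is the only place that names tests for the trial data: Student's "T test for analysis of continuous variables, Chi square test for categorical variables", with "significance level set at two tailed p value of <0.05". It names no rank, trend or ordinal method and does not assign a test to any endpoint.
- **Timing.** The aim 2 text in Section 13 (and in the synopsis) has post-embolization syndrome assessed "at least twice during the day of the procedure and then daily for the next 3 days and then at 7 days", which is at least 2 + 3 + 1 = 6 assessments. The post-procedure list in Section 13 records nausea and vomiting at time 0 and then at 3 + 3 + 2 + 3 + 1 = 12 further times. No analysis time or summary score is named.
- **Size.** Section 9: "sample size of 21 per group will provide us with 86% statistical power to detect such an effect size". That calculation is for the pain score only. No expected distribution, effect size or power is given for nausea or vomiting.

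**The concern.** A 0-3 severity grade is neither clearly continuous nor simply categorical in the sense of Section 16. The verb *categorize* in Section 12 makes a 2x4 chi-square a live reading. That test has 3 degrees of freedom, gives the same answer however the grades are ordered, and has small expected counts with 21 per arm. A treatment that moves patients down the scale produces an ordered difference, and a test that ignores order spends its power on patterns nobody is looking for. Nausea and vomiting are at the centre of aim 2, and the trial was not sized for them, so power given up here makes a null result harder to interpret. Because the plan leaves the test and the time point open, the choice could also be made after the scores have been seen.

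**Working it through.** **1. The plan's own power figure (pain).** Section 9 takes a mean that "was 2.89 (SD 1.09) compared to 3.91 (SD 2) for controls".
- Pooled SD = √[(1.09² + 2²)/2] = √2.594 = 1.611.
- Difference = 3.91 − 2.89 = 1.02; enlarged by the plan's 50%, 1.53. Standardised effect = 1.53/1.611 = 0.95.
- Normal approximation: 0.95 × √(21/2) − 1.96 = 1.118, so power is 86.8%. The noncentral t with 40 df gives 85.2%.

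The stated 86% is reproduced. It says nothing about nausea or vomiting.

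**2. Inputs for the 0-3 scores.** From the documents: four ordered grades, two-sided 0.05, and "approximately 21 local participants in each arm of this trial" (Section 28). Assumed, because the documents are silent: the control distribution over grades 0/1/2/3, and a proportional-odds shift towards lower grades. One score per patient is analysed.

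**3. How the shift works.** With control cumulative probability C at or below a grade, the treated cumulative odds are OR × C/(1 − C). Example: control 25/25/25/25% and OR 4.
- Control cumulative odds are 1/3, 1 and 3; treated are 4/3, 4 and 12.
- Treated cumulative probabilities are 0.571, 0.800 and 0.923, so treated grades are 57.1/22.9/12.3/7.7%.
- Mean expected count per arm at grade 3 is 21 × (0.25 + 0.077)/2 = 3.4, and at grade 2 it is 21 × (0.25 + 0.123)/2 = 3.9. Both are below 5.

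**4. Power by simulation.** Each scenario used 40,000 trials, so the standard error is at most √(0.25/40,000) = 0.25 points. Chi-square is the uncorrected Pearson test on occupied grades; Wilcoxon is tie-corrected; the t test is Student's on the scores.

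| Control 0/1/2/3 (%) | OR | Chi-square | Wilcoxon | t test | Wilcoxon − chi-square |
|---|---|---|---|---|---|
| 25/25/25/25 | 2 | 15.2% | 23.2% | 23.5% | 8.0 |
| 25/25/25/25 | 3 | 32.1% | 48.2% | 48.3% | 16.1 |
| 25/25/25/25 | 4 | 48.7% | 66.7% | 66.4% | 18.0 |
| 20/30/30/20 | 4 | 48.5% | 67.1% | 67.0% | 18.6 |
| 40/30/20/10 | 5 | 52.3% | 72.1% | 69.5% | 19.8 |
| 10/20/30/40 | 5 | 63.4% | 80.1% | 80.6% | 16.7 |
| 60/20/15/5 | 5 | 35.0% | 57.1% | 53.6% | 22.1 |

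Over six control distributions the gap was 8 to 9 points at OR 2, 15 to 17 at OR 3, 18 to 20 at OR 4 and 17 to 22 at OR 5. A separate run with OR 2.5 gave about 13 there. Beyond that range it was 14 to 24 at OR 6 and 9 to 24 at OR 8.

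Wilcoxon minus t test ran from −0.6 to +4.2 points over all proportional-odds scenarios. With no effect, the Wilcoxon test rejected in about 5% of trials and chi-square in 3.7% to 5.1%, so the gain does not come from a loose rank test. At least 96% of simulated tables had an expected count below 5.

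**5. Shifts that are not proportional.** For four shifts confined to particular grades, chi-square beat Wilcoxon by 13 to 41 points. Example: control 10/20/30/40% against 10/20/65/5% gives 73.9% for chi-square and 32.6% for Wilcoxon. Moving a whole worst grade of 25% one step down, from 25/25/25/25% to 25/25/50/0%, gives about 60% against 11%.

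**The case against.** A reader might infer that the plan prescribes chi-square for these scores, so that the loss is built in. The documents do not support that. Section 12 calls the 0-3 scale numerical and contrasts it with the yes/no item, and Section 13 groups nausea and vomiting with the pain scores, which Section 9 sizes with a t test. Sending the scores to the t test is at least as natural a reading, and it loses little. A third reading comes from Section 6, which hypothesises a lower incidence of nausea and vomiting. That could mean any against none, where chi-square is appropriate. Its power in the same simulations depends on the distribution: 59% against 57% for Wilcoxon with control 60/20/15/5% and OR 5, but 40% against 68% with control 10/20/30/40% and OR 4.

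A reader might also infer that a rank test costs nothing. Step 5 shows otherwise: proportional odds favours the rank test, and some other patterns favour chi-square.

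Finally, these are secondary endpoints, and most Wilcoxon powers at OR 2 to 4 are below 70%, so a null result would be hard to read with either test. Naming a test also leaves open which of the repeated scores is compared.

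All of this stands, and it limits the size of the point. It does not remove it: the three readings give materially different power, and the plan does not choose between them.

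**Conclusion.** The point holds as an unspecified analysis with a conditional cost. With 21 per arm and an assumed consistent (proportional-odds) shift, a four-grade chi-square has about 8 to 9 points less power than Wilcoxon at OR 2 and about 13 to 22 points less at OR 2.5 to 5. If the t test is used, the difference is at most about 4 points. These figures rest on assumed grade distributions and ORs and on one score per patient, so they show the scale of the issue and do not predict this trial's power. The documents do not establish that the trial as written will lose this power, only that it may. The matter concerns a secondary endpoint and does not touch the sample size or the pain analysis. It is a cheap improvement worth making before the data are analysed.

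**What to change.** Add to Section 16: the 0-3 nausea and vomiting scores are compared between arms by the Wilcoxon rank-sum test (or a proportional-odds model, which also gives an odds ratio), each on one named summary, such as the worst score over a stated window. State that window, since the scores are repeated and the two schedules in Section 13 differ in density. Keep chi-square for yes/no items such as fever or chills and readmission.

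The cost is a sentence or two of text. No patients or data are added, and the test is available in the named software. The statistical downside is lower power than chi-square if the effect is confined to one grade. That is acceptable here because the stated hypothesis is directional: less nausea and vomiting with dexamethasone.
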